### **Continuing on Monotherapy**

If a patient discontinues osimertinib due to toxicity the patient may continue with savolitinib until progression.

If a patient discontinues savolitinib due to toxicity they may continue with osimertinib monotherapy until the Principal Investigator believes there is no further benefit (this may be beyond PD in the absence of clinical symptoms or signs indicating clinically significant PD; no decline in performance status; absence of rapid PD or threat to vital organs or critical anatomical sites [eg, central nervous system metastasis, respiratory failure due to tumour compression, spinal cord compression] requiring urgent alternative medical intervention; or no significant, unacceptable or irreversible toxicities related to study intervention), according to the SoAs ([Table 1](#) and [Table 2](#)).

Following PD, patients may continue on osimertinib monotherapy and continue with all safety assessments as per the SoAs ([Table 1](#) and [Table 2](#)). Savolitinib monotherapy (either if originally randomised to savolitinib plus placebo or after discontinuation of osimertinib if originally randomised to savolitinib plus osimertinib) post progression is not permitted.

#### **7.1.1 Rechallenge**

See guidance in [Appendix I](#) for circumstances under which a patient whose study intervention was temporarily interrupted due to an AE can restart treatment, and specifically additional precautions to be taken upon restarting savolitinib.

#### **7.1.2 Procedures for Discontinuation of Study Intervention**

The investigator should instruct the patient to contact the site before or at the time if any study intervention is stopped. A patient that decides to discontinue study intervention(s) will always be asked about the reason(s) and the presence of any AEs. The date of last intake of study intervention(s) should be documented in the eCRF. All study intervention(s) should be returned by the patient at their next on-site study visit or unscheduled visit. Patients permanently discontinuing study intervention should be given locally available standard of care therapy, at the discretion of the investigator.

Discontinuation of study intervention(s), for any reason, does not impact on the patient's involvement in the study. The patient should continue attending subsequent study visits and data collection should continue according to the CSP. If the patient does not agree to continue in-person study visits, a modified follow-up must be arranged to ensure the collection of endpoints and safety information. This could be a telephone contact with the patient, a contact with a relative or treating physician, or information from medical records. The approach taken should be recorded in the medical records. A patient that agrees to modified follow-up is not considered to have withdrawn consent or to have withdrawn from the study.

As a minimum, telephone contact should be made with the patient 28 days following the discontinuation of both study interventions to collect new AEs and follow up on any ongoing AEs and concomitant medications (including any subsequent cancer therapy, if appropriate). Refer to Section 8.3.2 for full details on AE recordings during follow-up.

## 7.2 Patient Withdrawal from the Study

- A patient may withdraw from the study at any time at his/her own request, or may be withdrawn at any time at the discretion of the investigator for safety, behavioural, compliance or administrative reasons. This is expected to be uncommon.
- A patient who considers withdrawing from the study must be informed by the investigator about modified follow-up options (eg, telephone contact, a contact with a relative or treating physician or information from medical records).
- At the time of withdrawal from the study, if possible, an Early Study Intervention Discontinuation visit should be conducted, as shown in the SoAs (Table 1 and Table 2). See the SoAs for data to be collected at the time of study withdrawal and follow-up and for any further evaluations that need to be completed.
  - The patient will discontinue the study intervention and be withdrawn from the study at that time.
- If the patient withdraws consent for disclosure of future information, the sponsor may retain and continue to use any data collected before such a withdrawal of consent.
- If a patient withdraws from the study, it should be confirmed if he/she still agrees for existing samples to be used in line with the original consent. If he/she requests withdrawal of consent for use of samples, destruction of any samples taken and not tested should be carried in line with what was stated in the informed consent and local regulation. The investigator must document the decision on use of existing samples in the site study records and inform the Global Study Team.

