## 5 STUDY POPULATION

Prospective approval of CSP deviations to recruitment and enrolment criteria, also known as CSP waivers or exemptions, is not permitted.

Each patient should meet all of the inclusion criteria and none of the exclusion criteria for this study in order to be enrolled on the study. Under no circumstances can there be exceptions to

this rule. Patients who do not meet the entry requirements are screen failures, refer to Section 5.4.

For procedures for withdrawal of incorrectly enrolled patients see Section 7.2.

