## **7 DISCONTINUATION OF STUDY INTERVENTION AND PATIENT DISCONTINUATION/WITHDRAWAL**

### **7.1 Discontinuation of Study Intervention**

It may be necessary for a patient to permanently discontinue (definitive discontinuation) study intervention. If study intervention is permanently discontinued, the patient will remain in the study to be evaluated for survival.

Patients may be discontinued from study intervention in the following situations. Note that discontinuation from study intervention is NOT the same thing as a withdrawal from the study.

- Patient decision. The patient is at any time free to discontinue treatment, without prejudice to further treatment.
- Adverse events.
- Severe non-compliance with the CSP.
- Disease progression as per RECIST 1.1; unless the patient is randomised to savolitinib plus placebo, when cross-over to savolitinib plus osimertinib may be permitted.

- Patients incorrectly initiated on study medication.
- Pregnancy.
- Specific stopping criteria, ie, ILD, acute anaphylaxis or QTcF interval prolongation with signs/symptoms of serious arrhythmia.

See the SoAs ([Table 1](#) and [Table 2](#)) for data to be collected at the time of intervention discontinuation and follow-up and for any further evaluations that need to be completed.

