## 8.1 Efficacy Assessments

### 8.1.1 CT and MRI Scans Tumour Assessments (RECIST 1.1)

The RECIST 1.1 guidelines for measurable, non-measurable, TLs and NTLs and the objective tumour response criteria are presented in [Appendix H](#) of this CSP.

Baseline tumour assessments should include CT/MRI of chest and abdomen (including liver and adrenal glands) and should be performed within 28 days of randomisation, and ideally as close as possible to the start of study intervention. At screening the MRI/CT scans will include brain imaging for all patients. Those determined to have brain metastases will have their brain rescanned at all subsequent tumour assessments. Any other regions suspected, or with known metastasis at baseline, will be assessed by imaging and recorded at baseline. The same imaging modality used for baseline tumour assessment should be used for each subsequent follow-up assessment throughout the study if possible. Further details of the CT and MRI acquisition parameters will be documented in a separate image acquisition guidelines document.

Follow-up assessments should be performed Q6W ( $\pm 7$  days) after randomisation until Cycle 7 (up to 24 weeks), and then Q8W ( $\pm 7$  days) until objective PD as defined by RECIST 1.1 even if a patient discontinues treatment prior to progression (unless they withdraw consent). For patients who cross-over based on confirmed objective disease progression during the initial randomised treatment period (including patients who have already crossed over based on confirmed PD prior to CSP Version 3.0), scheduled RECIST 1.1 tumour assessments are not required, and the subsequent assessment of disease progression will be based on standard-of-care scan or investigator determined clinical progression. Scheduled RECIST 1.1 tumour assessments are required (the scan frequency is against initial randomisation) for patients who cross-over after study unblinding and who have not objectively progressed during the initial randomised treatment period. Patients who cross-over after study unblinding, who have no objective progression during initial randomisation period, and who discontinue study intervention after cross-over for reasons other than investigator-confirmed disease progression will continue scheduled RECIST 1.1 tumour assessments until objective disease progression per RECIST 1.1 as assessed by investigator, unless they withdraw consent to the entire study.

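### Section 7.2 lets the investigator end study participation without withdrawal of consent, in conflict with Sections 7.1, 7.1.2 and 8.1.1, so PFS and DoR follow-up may be lost

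*Supplement*

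**What the plan says.** Section 7.2 gives two routes out of the study. One is the patient's own request. In the other, the patient "may be withdrawn at any time at the discretion of the investigator for safety, behavioural, compliance or administrative reasons". Of withdrawal it says "This is expected to be uncommon", and of its effect: "The patient will discontinue the study intervention and be withdrawn from the study at that time". Alternative follow-up is written for one case only: "A patient who considers withdrawing from the study must be informed by the investigator about modified follow-up options". Nothing equivalent is written for a patient whom the investigator removes.

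Section 5 adds: "For procedures for withdrawal of incorrectly enrolled patients see Section 7.2". Section 7.2 contains no text specific to such patients.

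Other sections separate stopping treatment from leaving the study. Section 7.1 lists adverse events, severe non-compliance and incorrect initiation of study medication as grounds for stopping treatment, and says: "If study intervention is permanently discontinued, the patient will remain in the study to be evaluated for survival". Section 7.1.2 says: "Discontinuation of study intervention(s), for any reason, does not impact on the patient's involvement in the study". Section 8.1.1 runs RECIST scans to objective progression "even if a patient discontinues treatment prior to progression (unless they withdraw consent").

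**The concern.** Safety and compliance problems can be handled in two ways. Under 7.1 the patient stops drug and is followed. Under 7.2 the patient stops drug and leaves the study. The choice is the investigator's, and no criterion separates the two.

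This matters most for PFS and DoR, both secondary endpoints. Patients withdrawn for toxicity or poor compliance may have a different prognosis from those who stay, so censoring them at the last scan may not be independent of outcome. The two arms also carry different drugs, so the rate of such withdrawal could differ between them. Scans not taken cannot be recovered later. The protocol says that the full analysis set follows intention to treat, and that depends on outcome data being collected after treatment stops.

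**Working it through.** The plan states no figure for withdrawal or dropout, so there is none to reproduce. The check sets the sections side by side, traces the effect on each endpoint, and then sizes it under stated assumptions.

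**1. One situation, different outcomes**
- Adverse event or safety reason: 7.1 stops treatment and the patient stays; 7.2 allows removal from the study.
- Non-compliance: the same split.
- Wrongly entered patient: 7.1 stops treatment if drug was started; Section 5 points to 7.2.
- Scans: 8.1.1 exempts only withdrawal of consent; 7.2 ends participation without it.
- A related case: for toxicity unresolved after 3 weeks of withholding osimertinib, Appendix I 2 says that the patient should leave the study, while Table I1 only discontinues the drug.

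**2. Effect on each endpoint if 7.2 is followed literally**
- PFS (9.4.2.2): with no event, censored at the last evaluable RECIST assessment. Progression or death after two or more missed visits is censored too, so a death found later by vital-status search may not restore the event.
- DoR: takes over the PFS censoring time.
- ORR (9.4.2.1, Table 11): the patient stays in the full analysis set. A recorded response counts; only a later one is missed.
- OS: vital status is sought for all randomised patients (7.3) and for those withdrawn from the study (8.1.2).

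**3. Worst case for 6-month PFS in one arm**

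The number of patients actually randomised is not given. I assume 10, 14 or 28 per arm (28 was planned), exponential PFS with a 6-month median, and follow-up cut at 12 months. One or two patients who would progress within 6 months are instead censored one month before progression.

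A hand bracket for the Kaplan-Meier estimate: let n/2 patients be due to progress by 6 months, with m of them censored instead. If all m are censored before any event, the estimate is (n/2)/(n − m). If all are censored after the remaining events, it is (n/2 + m)/n.
- m=1: n=10, 5/9 to 6/10 = 55.6% to 60.0%; n=14, 7/13 to 8/14 = 53.8% to 57.1%; n=28, 14/27 to 15/28 = 51.9% to 53.6%.
- m=2: n=10, 5/8 to 7/10 = 62.5% to 70.0%; n=14, 7/12 to 9/14 = 58.3% to 64.3%; n=28, 14/26 to 16/28 = 53.8% to 57.1%.

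Simulation (4,000 runs per cell) falls inside these brackets. From about 50%, one patient gives 57%, 54% and 52% for n = 10, 14 and 28; two give about 65%, 60% and 55%. With one or two random patients withdrawn at random times, the estimate stays at 50% in every cell.

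**4. Hazard ratio**

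Large-sample simulation: assumed 4-month median on savolitinib plus placebo, 6-weekly scans, every withdrawn patient censored at the last scan before progression.
- Withdrawal of 5%, 10% and 20% in the combination arm only: a true HR of 1.0 appears as about 0.95, 0.91 and 0.82; a true 0.6 as about 0.58, 0.55 and 0.50.
- The same rates in both arms: 0.996 to 1.002, and 0.59 to 0.60.

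Of 28 patients, 5%, 10% and 20% are 1.4, 2.8 and 5.6.

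**5. ORR**

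If a share w leaves before responding, and leaving is unrelated to response, observed ORR = true ORR × (1 − w). With 30% for illustration (the combination figure from an earlier study, Section 4.2.1) and w = 5%, 10% and 20%, this gives 28.5%, 27.0% and 24.0%.

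**The case against.** The strongest reply is that nothing in the protocol says imaging stops for these patients. Section 8.1.1 exempts only withdrawal of consent, the tumour-imaging footnote to Table 1 continues scans after any discontinuation other than for progression, and 7.2 itself refers to the schedule of activities for follow-up after withdrawal. This stands. A reader might infer that scans do stop; the documents support only an unresolved conflict.

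A reader might also put ORR, the primary endpoint, on the same footing as PFS. That fails, because the patient stays in the denominator and any recorded response counts.

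The worst-case figures assume that every withdrawn patient was about to progress, and the documents give no evidence for that. They describe one arm, not the comparison. This stands too.

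Withdrawal is expected to be uncommon, recruitment has ended, and Section 9.4.1.2 says that the study is not designed to support labelling claims. This limits the weight of the point but does not settle which section a site should follow. No SAP is shown, and further sensitivity analyses are left to it, so their absence is no finding.

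Limiting withdrawal strictly to consent or loss to follow-up would go too far. Appendix A 9 foresees site closure with transfer only if feasible, so some administrative cases cannot be followed.

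**Conclusion.** The point holds as a conflict in the text. Section 7.2, with the cross-reference from Section 5, allows removal from the study for reasons that 7.1 treats as grounds to stop treatment only. It needs no withdrawal of consent and states no follow-up, while 8.1.1 requires scans to objective progression.

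The exposure is mainly PFS and DoR, and its size is unknown. One ill-placed withdrawal could move 6-month PFS in one arm by about 2 points (n=28) to 7 points (n=10), given an assumed 6-month median and censoring one month before progression. It would not be right to conclude that PFS will be biased: withdrawal unrelated to prognosis causes no shift, and the HR is distorted only when withdrawal is both prognostic and unequal between arms. It is a risk worth closing because the arms are small and the wording change is cheap.

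**What to change.** In Section 7.2, state that investigator decisions for safety, behavioural or compliance reasons, and decisions about incorrectly enrolled patients, are discontinuation of study intervention under 7.1. RECIST assessments to objective progression and survival follow-up then continue under 8.1.1 and 8.1.2 while the patient consents. Keep study withdrawal for withdrawal of consent, loss to follow-up under 7.3, and administrative cases where follow-up is not feasible, such as site closure without transfer. Amend the cross-reference in Section 5 to match. Reconcile Appendix I 2 with Table I1, which give different outcomes for the same unresolved toxicity.

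The cost is a short text change in 7.2, one cross-reference, and continued scheduled follow-up of a few patients. Patients keep their right to withdraw.

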## 7.3 Lost to Follow up

A patient will be considered lost to follow-up if he or she repeatedly fails to return for scheduled visits and is unable to be contacted by the study site.

The following actions must be taken if a patient fails to return to the clinic for a required study visit:

- The site must attempt to contact the patient and reschedule the missed visit as soon as possible and counsel the patient on the importance of maintaining the assigned visit schedule and ascertain whether or not the patient wishes to and/or should continue in the study.
- Before a patient is deemed lost to follow up, the investigator or designee must make every effort to regain contact with the patient (where possible, 3 telephone calls and, if necessary, a certified letter to the patient's last known mailing address or local equivalent methods). These contact attempts should be documented in the patient's medical record.
- Should the patient continue to be unreachable, he/she will be considered to have withdrawn from the study.
- Site personnel, or an independent third party, will attempt to collect the vital status of the patient within legal and ethical boundaries for all patients randomised, including those who did not get study intervention. Public sources may be searched for vital status information. If vital status is determined as deceased, this will be documented and the patient will not be considered lost to follow-up. Sponsor personnel will not be involved in any attempts to collect vital status information.

Discontinuation of specific sites or of the study as a whole are handled as part of [Appendix A](#).

## **8 STUDY ASSESSMENTS AND PROCEDURES**

- Study procedures and their timing are summarised in the SoAs ([Table 1](#) and [Table 2](#)). Protocol waivers or exemptions are not allowed.
- Immediate safety concerns should be discussed with the sponsor immediately upon occurrence or awareness to determine if the patient should continue or discontinue study intervention.
- Adherence to the study design requirements, including those specified in the SoAs ([Table 1](#) and [Table 2](#)), is essential and required for study conduct.
- All screening evaluations must be completed and reviewed to confirm that potential patients meet all eligibility criteria. The investigator will maintain a screening log to record details of all patients screened and to confirm eligibility or record reasons for screening failure, as applicable.
- Procedures conducted as part of the patient's routine clinical management (eg, blood count) and obtained before signing of the ICF may be utilised for screening or baseline purposes provided the procedures met the CSP-specified criteria and were performed within the time frame defined in the SoAs ([Table 1](#) and [Table 2](#)).

## 8.1 Efficacy Assessments

### 8.1.1 CT and MRI Scans Tumour Assessments (RECIST 1.1)

The RECIST 1.1 guidelines for measurable, non-measurable, TLs and NTLs and the objective tumour response criteria are presented in [Appendix H](#) of this CSP.

Baseline tumour assessments should include CT/MRI of chest and abdomen (including liver and adrenal glands) and should be performed within 28 days of randomisation, and ideally as close as possible to the start of study intervention. At screening the MRI/CT scans will include brain imaging for all patients. Those determined to have brain metastases will have their brain rescanned at all subsequent tumour assessments. Any other regions suspected, or with known metastasis at baseline, will be assessed by imaging and recorded at baseline. The same imaging modality used for baseline tumour assessment should be used for each subsequent follow-up assessment throughout the study if possible. Further details of the CT and MRI acquisition parameters will be documented in a separate image acquisition guidelines document.

Follow-up assessments should be performed Q6W ( $\pm 7$  days) after randomisation until Cycle 7 (up to 24 weeks), and then Q8W ( $\pm 7$  days) until objective PD as defined by RECIST 1.1 even if a patient discontinues treatment prior to progression (unless they withdraw consent). For patients who cross-over based on confirmed objective disease progression during the initial randomised treatment period (including patients who have already crossed over based on confirmed PD prior to CSP Version 3.0), scheduled RECIST 1.1 tumour assessments are not required, and the subsequent assessment of disease progression will be based on standard-of-care scan or investigator determined clinical progression. Scheduled RECIST 1.1 tumour assessments are required (the scan frequency is against initial randomisation) for patients who cross-over after study unblinding and who have not objectively progressed during the initial randomised treatment period. Patients who cross-over after study unblinding, who have no objective progression during initial randomisation period, and who discontinue study intervention after cross-over for reasons other than investigator-confirmed disease progression will continue scheduled RECIST 1.1 tumour assessments until objective disease progression per RECIST 1.1 as assessed by investigator, unless they withdraw consent to the entire study.

It is important to follow the assessment schedule as closely as possible. If scans are performed outside of the scheduled visit  $\pm 1$  week window interval and the patient has not progressed, every attempt should be made to perform the subsequent scans at their scheduled time points. Patients will be evaluated until objective radiological PD by RECIST 1.1 as per the SoAs ([Table 1](#) and [Table 2](#)).

Categorisation of objective tumour response at each visit will be based on the RECIST 1.1

guidelines for response: CR, PR, SD, NE and PD.

Target lesion progression will be calculated in comparison to when the tumour burden was at a minimum (ie, smallest sum of diameters previously recorded on study). In the absence of progression, tumour response (CR, PR, SD, NE) will be calculated in comparison to the baseline tumour measurements obtained before starting treatment.

If the investigator is in doubt as to whether progression has occurred, particularly with response to NTLs or the appearance of a new lesion, it is advisable to continue treatment and reassess the patient's status at the next scheduled assessment or sooner if clinically indicated.

To achieve 'unequivocal progression' on the basis of non-target disease, there must be an overall level of substantial worsening in non-target disease such that, even in presence of SD or PR in target disease, the overall tumour burden has increased sufficiently to merit unequivocal progression by NTLs. A modest 'increase' in the size of one or more NTLs is usually not sufficient to qualify for unequivocal PD status.

If repeated scans confirm progression, then the date of the initial scan should be declared as the date of progression.

All CT/MRI scans and all imaging assessments performed for RECIST 1.1 tumour assessment will be reviewed at site. All images, including unscheduled visit scans, will be collected on an ongoing basis and sent to an AstraZeneca-appointed CRO to enable BICR up to the point of the final analysis (the earlier of 18 months after the last patient is randomised or when 70% of patients have progressed or died). Guidelines for image acquisition, de-identification, storage at the investigative site as source data, and transfer to the imaging CRO will be provided in a separate document. Further details of the BICR will be documented in the Independent Review Charter (also referred to as "Imaging Charter"). Results of the independent reviews will not be communicated to investigators, and results of investigator RECIST 1.1 assessments will not be shared with the central reviewers. The management of patients will be based wholly upon the results of the RECIST 1.1 assessment conducted by the investigator.

Following investigator-assessed PD, in patients who cross-over from savolitinib plus placebo to receive the combination of savolitinib and osimertinib, secondary ORR, PFS, DoR and change in tumour size assessments will be performed by the investigator using imaging assessments per RECIST 1.1 (see Section 9.4.2.3). These local-practice scans should not be sent to the appointed CRO for BICR.

